### **Outcomes and instruments**

Observation, interview, and measurement methods were used to collect the data. “Brief Fatigue Inventory (BFI)” and “Descriptive Information Form” were used to evaluate the fatigue level of the patients on the first, ninth, and twenty-first days. The patients’ demographic and medical characteristics were obtained from their medical records.

*The Descriptive Information Form:* This form was used to collect information on the sociodemographic characteristics, diseases, and treatments of the patients.

*The Brief Fatigue Inventory (BFI):* This inventory was developed by Mendoza et al. (1999) to evaluate the general fatigue level and its effect on activities of daily living in patients with

cancer. The study evaluating its validity and reliability for the Turkish context was carried out by Çınar et al.(2000) Cronbach's alpha internal consistency coefficient of the inventory was found as 0.98. The BFI consists of nine items in total, with three evaluating general fatigue and six evaluating the effect of fatigue on daily life. Individuals rate all items on a scale of "0" (no fatigue) to "10" (the most severe fatigue you can experience), taking into account their status in the last 24 hours. The "general fatigue" level is calculated by taking the average of the first three items of the inventory. The average of the last six items yields a score for the effect of fatigue on the activities of daily living. According to the scores obtained from the BFI, the severity of fatigue of the individual was "0, no fatigue; 1-3, mild; 4-6, moderate; and 7-10, severe fatigue".

### **Interventions**

Descriptive Information Form and the BFI were administered to the patients in both groups on the first day of the application phase, and their baseline assessment was made, which was followed by interventions for energy conservation (organizing the patient's sleep-rest hours, supporting activities of daily living, organizing the living environment, etc.) and energy enhancement (adequate and balanced nutrition). The patients were informed about the study procedure. Between the second and the eighth days of the application phase, the patients in the intervention group were administered a standard white light at 10,000 Lux intensity by an independent nurse (RA1) in their home environment using a Litebook Elite light source (The Litebook Company Ltd., Medicine Hat, AB). The distance between the light source and the patient's face was set at 50 cm, and the intensity of the light for each patient was checked using a Lux Meter. The intervention was applied between 07:00 and 10:00 in the morning for 30 minutes without interruption, and it was continued for seven successive days. The light application procedure was followed based on the previous studies on oncology patients. [16,25] The patient was asked to engage in other activities during the light administration, such as

watching television, reading books, and not to look directly at the light. The second and third evaluations of the fatigue status of both groups of patients were completed on the 9th and 21st days by an independent other nurse (RA2).

### **Data analysis**

The statistical analysis was performed on IBM SPSS v.24 (SPSS, Chicago, IL) software package. To compare the socio-demographic characteristics of groups, independent groups t-test and chi-square analysis were used. Paired samples t-test was used to determine differences between the study groups, and analysis of variance (repeated measurements ANOVA) was employed in repeated measurements. To ensure the balance between the groups and the reliability of the intervention results, the intention-to-treat method was not used in the analyses. Statistical significance level was accepted as  $p < 0.05$ .

2. Çınar S, Sezerli M, Sarsmaz N, Menteş AÖ. Hemodiyaliz akut yorgunluk sendromuna neden olabilir mi. *Hemşirelik Forumu Derg*. 2000;3:28–33.
3. Broglio K. Randomization in clinical trials: permuted blocks and stratification. *Jama*. 2018;319(21):2223–4.

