# **The Effect of White Light on Fatigue Levels in Patients With Gynecological Cancer: A Double Blind Randomized Trial**

**02.08.2021**

## **STUDY PROTOCOL**

### **Study design and participants**

[figure not shown]
This was a triple-blind randomized study. The study included two parallel groups consisted of 72 patients who met the inclusion criteria and were receiving outpatient chemotherapy for gynecological cancer. The sample size in this study was 72 subjects: 36 in the intervention group and 36 in the control group. This study was based on an effect size of 0.25, a first type error of 5%, and 80% power, relying on the results of a previous study that evaluated the effect of bright white light on the fatigue levels of patients with cancer.[16] Patients aged over 18 years, had a normal state of consciousness, had no communication disorders, did not work in the night shift, had a general fatigue level score of  $\geq 1$  according to the Brief Fatigue Inventory(1,2), and could perceive light were included in the study. Patients who had natural/artificial lenses, used medication that causes photosensitivity (tetracycline, doxycycline, nalidixic acid, voriconazole, amiodarone, hydrochlorothiazide, naproxen, piroxicam, chlorpromazine), and had a change in their treatment plan in the last 6 weeks were not included in the study.

A total of 132 women were admitted to the clinic at the time of the study. All of them were evaluated as per the conditions of inclusion criteria. Twenty-five women who did not meet the inclusion criteria and another 12 who refused to participate in the study were not included in the study. Therefore, a total of 89 women, 47 in the intervention group and 42 in the control group, were included in the study through randomization. However, six women from the intervention group and three from the control group were excluded from the study because of various reasons such as rejecting white light administration, familial reasons, and reaching saturation in stratification according to the fatigue level factor. Thus, the study was conducted

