### **Randomization and blinding**

The study participants were stratified into intervention and control groups using stratified and block randomization methods, respectively. Firstly, patients who met the inclusion criteria and accepted to participate in the study were stratified according to the severity of fatigue (1-3 points, mild; 4-6 points, moderate; 7-10 points, severe fatigue). For block randomization, at least 10 blocks were selected by random drawing among 20 blocks (permutations block 6 and block of size 3 with 1:1) produced by the researchers on SAS 9.4 (SAS Institute Inc., Cary, NC) software package (3-5). Random assignment was continued until there were an equal number of patients (12 patients in each 3 strata) according to their fatigue levels in each group, and the groups consisted of 36 patients (Figure).

**Figure.** Diagram of participant flow through study

A researcher among the authors who was not involved in patient care and implementation of interventions evaluated patients for eligibility, enumerated them, collected baseline data, and assigned them to research groups. Moreover, this researcher assigned the research groups at the beginning of the research, the intervention group “A,” whereas the control group was coded with the letters “B.” Two research assistants (RA) were recruited and trained for this study. Research assistants were two nurses with a bachelor’s degree, who were independent of each other and the researchers. The groups to which the patients belonged were reported to the nurses using the appropriate letter code. The first nurse (RA1) who made the interventions to the intervention group. The post-intervention evaluation of the patients in the application and control groups and the entry of the obtained data into the statistics program were made by the other nurse (RA2) who was not informed about the application. Thus, the nurse (RA2) who conducted the evaluations, were blinded. During data entry, coding of the groups was continued. A biostatistician, who was unaware of the purpose of the research, interventions, and groups, performed statistical analysis on the research data. Further, the coding of the groups was terminated by the authors at the end of the analysis. In this manner, double blinding was achieved in the study.

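### The plan assigns a paired t-test to two unmatched arms and gives its repeated-measures ANOVA no group or group-by-time term, so no valid between-arm test of BFI is stated

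*Combined protocol and SAP*

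**What the plan says.** The Data analysis section is the whole analysis plan. It makes three assignments of tests:

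- Independent-samples t-test and chi-square: for comparing the arms on socio-demographic characteristics.
- Paired t-test: "Paired samples t-test was used to determine differences between the study groups".
- Repeated-measures ANOVA: "and analysis of variance (repeated measurements ANOVA) was employed in repeated measurements". No group factor, interaction or contrast is given.

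BFI is not tied by name to any of these tests, and no other section states a between-arm test.

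The design is described elsewhere. Study design and participants: "The study included two parallel groups consisted of 72 patients", with "36 in the intervention group and 36 in the control group". Randomization and blinding: "The study participants were stratified into intervention and control groups using stratified and block randomization methods", ending with 12 women per fatigue stratum in each arm. Outcomes and instruments: the BFI and the descriptive form "were used to evaluate the fatigue level of the patients on the first, ninth, and twenty-first days". Interventions: both arms completed the forms on day 1, "and their baseline assessment was made, which was followed by interventions for energy conservation", with nutritional support as well. Only the intervention arm then received light, on days 2 to 8.

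**The concern.** A paired t-test needs each value in one set to have a defined partner in the other. Stratified block randomization balances the arms on fatigue severity, but it does not match individual women, and no matching is described. The test named for the between-arm difference therefore does not fit the design.

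The sentence can be read in three ways, and none gives a stated, valid comparison:

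- **(a) Paired test across arms, as literally written.** The pairs are whatever the row order of the data file makes them.
- **(b) Paired pre-post tests within each arm, with the two p-values then contrasted.** The plan does not state this use; it is inferred as a likely meaning. It tests change within an arm, not light against control. Both arms receive the day-1 energy interventions, so both may change without any light effect.
- **(c) Repeated-measures ANOVA.** This is valid for comparing the arms if group-by-time is fitted and tested. The plan does not say so, and it assigns between-group differences to another test.

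Light against control on BFI is the trial's question. The reader cannot tell which analysis answers it, and under (b), or under (c) without the interaction, a change common to both arms could be credited to light.

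**Working it through.** The plan gives no figure on this point to reproduce. From the documents: 36 women per arm, unmatched; BFI on days 1, 9 and 21; significance at p < 0.05. Assumed, because the documents do not give them: no light effect; two-sided tests; normal data; a true change d common to both arms, in SD units of the change; correlations of 0.5 where needed.

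**Use (a): paired test across arms.** With equal SDs in the arms, t_paired = t_ind / √(1 − r), where r is the correlation that the row order happens to create. The paired test has 36 − 1 = 35 df; the independent test has 72 − 2 = 70.

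- Independent p = 0.05 means t_ind = 1.994. Paired significance needs t above 2.030, so 1 − r < (1.994/2.030)² = 0.965, or r > 0.035.
- Over random orders, r has SD 1/√35 = 0.169. P(r > 0.035) = P(Z > 0.21), about 0.42.
- The central 95% of orders has r within ±1.96 × 0.169 = ±0.331. At r = +0.331, t = 1.994/√0.669 = 2.44, p about 0.020. At r = −0.331, t = 1.994/√1.331 = 1.73, p about 0.09.
- Simulation (100,000 shuffles) agrees: 0.020 to 0.092, with 42% of orders below 0.05.
- Type I error is 4.9% paired and 4.9% independent; power at 0.5 SD is 54% and 55% (100,000 runs). Arbitrary pairing does not inflate error and costs little power.

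**Use (b): pre-post test in each arm, one visit.** The noncentrality is d√36 = 6d on 35 df. Let p be the chance that one arm shows significant improvement. Light-only = p × P(control not significant), which is close to p(1 − p) and peaks at p = 0.5. At d = 0.33, for example, p = 0.486 and 0.486 × 0.514 = 0.250.

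The either-visit columns count a claim at day 9 or day 21, with changes correlated 0.5 (40,000 runs).

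| Common change d | p | Light-only, one visit | Light-only, either visit | Two-sample test favouring light, either visit |
|---|---|---|---|---|
| 0 | 0.025 | 2.4% | 4.5% | 4.3–4.6% |
| 0.10 | 0.084 | 7.7% | 13% | 4.3–4.6% |
| 0.20 | 0.214 | 16.8% | 27% | 4.3–4.6% |
| 0.33 | 0.486 | 25.0% | 39% | 4.3–4.6% |
| 0.50 | 0.831 | 14.1% | 23% | 4.3–4.6% |
| 0.80 | 0.997 | 0.3% | 0.6% | 4.3–4.6% |

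A valid two-sided 5% test favours light falsely in 2.5% of trials at one visit. The one-visit light-only rate exceeds 5% for d from about 0.06 to 0.61.

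**Use (c): ANOVA over three visits** (20,000 runs, within-woman correlation 0.5, means 0, −d, −d; light-only counts improvements only).

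| d | Run per arm, light-only | Both arms pooled, time effect |
|---|---|---|
| 0 | 2.4% | 5% |
| 0.10 | 7% | 13% |
| 0.20 | 16% | 39% |
| 0.33 | 25% | 83% |
| 0.50 | 11% | 99% |
| 0.80 | 0.1% | 100% |

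The pooled time effect detects change over time and says nothing about light. With the group-by-time term, rejection is 4.8% to 5.1% throughout.

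**The case against.** The best defence is that the sentence is a drafting slip and the analysis was sound. Two arms by three visits suits a repeated-measures ANOVA with an arm factor. The sample size offers some support: for the between-groups effect with f = 0.25, three measurements and correlation 0.325, λ = 0.25² × 72 × 3 / (1 + 2 × 0.325) = 13.5/1.65 = 8.18 on 1 and 70 df, which gives power of about 0.80 at N = 72. The paired test may then have been meant as a within-arm description. This is plausible, but the plan states neither that metric nor that correlation, so it is only suggestive. If the slip was for a within-arm test, the plan still names no between-arm test.

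Several narrower objections stand:

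- Every inflation figure comes from a use the plan does not state. The 39% also needs a claim allowed at either visit, a common change near 0.33 SD and a correlation of 0.5. These figures show what the wording leaves open, not what happened.
- The 2.4% for the per-arm ANOVA at zero change counts improvements only; counting either direction, it is about 4.8%.
- The row-order result assumes random pairing. A file sorted by fatigue stratum would not be randomly paired. That does not rescue the test, because the answer would then depend on how the file was sorted: with r = 0.3 between rows, the same data give t = 1.994/√0.7 = 2.38 and p = 0.023 instead of 0.05.
- Naming a single primary score and day is a separate improvement. Preferring ANCOVA to a group-by-time model is a matter of choice, since both are valid.

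**Conclusion.** The concern holds and must be fixed. The stated test is wrong for the trial's main comparison, and the ANOVA as described does not repair it because its group and group-by-time terms are not stated. This follows from the documents alone and needs no assumption.

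The size of the harm is conditional. Under (a), the error rate is kept but borderline results turn on row order. Under (b), or an ANOVA run separately per arm, false credit to light reaches about 25% at one visit; under (b) it reaches about 39% at either visit. There is no inflation at a common change of 0 or 0.80 SD. If group-by-time was in fact tested, the result is sound and only the text is wrong. The documents cannot show which of these occurred.

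**What to change.** Replace the paired-test sentence with one such as: *Differences between the study groups in BFI are tested by ANCOVA at day 9 and day 21 with arm, baseline BFI and fatigue stratum, reported as the adjusted mean difference with 95% CI.* A repeated-measures model with group, time and group-by-time is an acceptable alternative, provided the interaction is named as the test of light against control. Keep paired t-tests only as within-arm description that supports no efficacy conclusion.

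As a separable addition, name one BFI score and one day as primary (for example general fatigue at day 9) and the rest as secondary. Label that choice post hoc if it is made after the data were seen.

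If a valid between-arm test was already run, correct the sentence to name it; no rerun is needed. Otherwise the cost is one sentence and a rerun on the existing day 1, 9 and 21 BFI data, with no new data and no burden on patients.

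### The repeated-measures ANOVA of fatigue at days 1, 9 and 21 has no stated rule for missing scores or for sphericity (minor)

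*Combined protocol and SAP*

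**What the plan says.** Outcomes and instruments states that the BFI and a descriptive form were used "to evaluate the fatigue level of the patients on the first, ninth, and twenty-first days". Under Interventions, light is given on days 2 to 8, and "The second and third evaluations of the fatigue status of both groups of patients were completed on the 9th and 21st days" by a nurse who was not told about the intervention.

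For the longitudinal comparison, Data analysis says that "analysis of variance (repeated measurements ANOVA) was employed in repeated measurements". It sets significance at p < 0.05, matching the sample-size statement of "a first type error of 5%, and 80% power". It also says that intention-to-treat was not used. It names no sphericity check or correction, no covariance structure, no rule for a missing score and no alternative model. A paired t-test is named too, but a paired test compares scores within a woman and does not replace the comparison between arms.

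Study design and participants reports 89 women randomised (47 and 42) and 72 in the study (36 and 36). Reasons given for exclusion after randomisation include "rejecting white light administration, familial reasons" and saturation of the fatigue strata. No section counts the women with a score at each visit.

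**The concern.** Two properties of the classical repeated-measures ANOVA matter here.

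- **Complete triplets.** The method needs all three scores from each woman. If day 21 is missing, her day-9 score also leaves the analysis, although it is the measurement closest to the end of treatment (the day after the last light session). Restoring all randomised women to the analysis set would not cure this, because the same ANOVA would drop the incomplete ones again.
- **Sphericity.** The uncorrected F-tests for time and group-by-time assume equal variances for the three pairwise visit differences. The visits are 8 and 12 days apart, and treatment falls between the first two, so there is no particular reason to expect this. When the assumption fails, the uncorrected test rejects too often. Group-by-time is the test of whether fatigue changes differently in the two arms.

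At stake are some precision at day 9 and a modest excess over the stated type I error.

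**Working it through.** **Inputs from the documents.** 36 women per arm; three visits (days 1, 9, 21); alpha 5%. The documents give no variances, correlations or visit-level missingness, so those below are assumptions shown as ranges. The sample-size statement ("This study was based on an effect size of 0.25") gives neither the effect-size metric nor a within-woman correlation. The figure of 72 can therefore be neither reproduced nor refuted, and nothing below depends on it.

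**Step 1: departure from sphericity.** With M the 2 × 2 covariance matrix of two orthonormal visit contrasts, epsilon = (tr M)² / (2 tr M²). It equals 1 under sphericity and cannot fall below 1/(3 − 1) = 0.5.

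Example with equal variances and correlations 0.7 (days 1–9), 0.7 (days 9–21) and 0.49 (days 1–21):
- Variances of the differences are 2(1 − 0.7) = 0.60, 0.60 and 2(1 − 0.49) = 1.02, so they are unequal.
- Linear contrast variance: (2 − 0.98)/2 = 0.51.
- Quadratic contrast variance: (6 − 2.8 − 2.8 + 0.98)/6 = 0.23.
- Covariance of the two contrasts: 0.
- Epsilon = 0.74² / (2 × (0.51² + 0.23²)) = 0.5476/0.626 = 0.875.

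**Step 2: type I error of the group-by-time test.** 100,000 null trials per covariance, 36 per arm, nominal 5%:

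| Assumed covariance | Epsilon | Uncorrected | Greenhouse-Geisser |
|---|---|---|---|
| All correlations 0.5 | 1.00 | 4.9% | 4.8% |
| Correlations 0.5, 0.5, 0.25 | 0.93 | 5.3% | 4.8% |
| Correlations 0.7, 0.7, 0.49 | 0.88 | 5.6% | 4.9% |
| Same, SDs 1, 1.25, 1.5 | 0.83 | 5.8% | 4.9% |
| Correlations 0.7, 0.7, 0.5; SDs 1, 1.5, 2 | 0.79 | 6.1% | 4.9% |
| Days 1–9 correlation 0.8, others 0.3 | 0.72 | 6.6% | 5.0% |

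The first row recovers the stated 5% when sphericity holds. The multivariate test also stays at 4.9% to 5.1%.

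**Step 3: exact ceiling.** At epsilon = 0.5 the statistic follows F(1, 70) but is compared with the 95th percentile of F(2, 140), which is 3.06. P(F(1, 70) > 3.06) = 8.46%.

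**Step 4: cost of losing day-9 scores (assumed rates).** If a fraction m of women have day 9 but not day 21, the day-9 standard error grows by 1/√(1 − m). A two-sample t-test with 36 per arm has 80% power at a standardised difference of 0.67.

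| m | n per arm | SE increase | Power |
|---|---|---|---|
| 0 | 36 | none | 80% |
| 5% | 34.2 | 2.6% | 78% |
| 10% | 32.4 | 5.4% | 76% |
| 20% | 28.8 | 11.8% | 70% |

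The documents do not show that m is above zero.

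**Step 5: why the replacement model needs day-1 BFI.** With equal variances and day-1 to day-9 correlation r, the day-9 standard errors are proportional to 1 (no baseline), √(2(1 − r)) (change score) and √(1 − r²) (baseline as covariate). At r = 0.7 these are 1, 0.775 and 0.714. A model without baseline then has a standard error 1/0.775 = 1.29 times that of the change score and 1/0.714 = 1.40 times that of the adjusted analysis.

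**The case against.** **The missed visit is hypothetical.** Interventions reports the day-9 and day-21 evaluations of both groups as completed, and assignment continued until each arm held 36 women. This largely stands. The sentence says when and by whom the assessments were made and gives no count of complete triplets, but it points towards completeness.

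**A reader might take 17/89 = 19% as the dropout rate.** The documents do not support that. These 17 are randomised women who are not among the 72. Only nine (six and three) are accounted for, and saturation of the strata is not a missed visit. Familial reasons carries no timing, so nothing shows that anyone left after day 9. A mixed model recovers nothing for these women unless they gave scores after baseline, which the documents do not say.

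**A reader might infer a biased result with doubled false positives.** Such a result can be constructed. Suppose about 22% of light women miss day 21, more often the fatigued ones, against 10% of controls, with 44 per arm and no true effect. A complete-case day-9 ANCOVA is then biased by −0.10 to −0.14 SD and rejects about 10% of the time. But the plan contains no day-9 ANCOVA. Under the same scenario the group-by-time F-test rejects about 6% to 7%, and the group main effect about 10% to 11%. The answer depends on the test and on a dropout pattern with no basis in the documents.

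**A reader might say that the plan assumes sphericity.** It is silent. The corrected and multivariate results are standard versions of the same analysis and hold about 5%. The group main effect does not depend on sphericity at all.

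**Conclusion.** The point holds as a gap in specification, and it is minor. The plan names a method that drops incomplete women and has an uncorrected version that exceeds 5%, and it settles neither matter.

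- **Type I error.** If the uncorrected group-by-time result is used, the excess is about 0.3 to 1.6 percentage points for the covariances tried and cannot exceed about 3.5 points. If a corrected or multivariate result is used, there is no material excess.
- **Lost day-9 scores.** The size is unknown and may be nil. If 5% to 20% of women had day 9 without day 21, a day-9 comparison with 80% power would fall to 78% to 70%.

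The covariances and missingness rates are assumptions. The documents do not establish that scores were lost, that the result is biased or that the uncorrected test was used.

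**What to change.** In Data analysis, make a likelihood-based linear mixed model of day-9 and day-21 BFI the main longitudinal analysis. Use fixed effects of arm, day, arm-by-day, day-1 BFI, day-1 BFI by day, and fatigue stratum, with an unstructured covariance. Include all available scores from every randomised woman. Day-1 BFI should not be left out: without it the model can be less precise than the planned ANOVA, and an observed predictor of missing visits is lost.

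Report by arm how many women have a score on each of days 1, 9 and 21. If the ANOVA is kept, state that the Greenhouse-Geisser-corrected group-by-time test is the one reported.

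The cost is wording, plus one model fit to data already collected if the analysis has been run. The model assumes that missing visits depend only on observed data, which is weaker than what the complete-case ANOVA needs but cannot be verified. If the visit counts show complete data and the covariance is near spherical, the missing-data and sphericity gains will be small.

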with a total of 72 women with 36 in each group (Figure). Patients and at least one of their relatives were informed about the research process and the use of white light in the patient room, along with visual materials. It was ensured that the informed consent form was ready by the patient and, if necessary, a relative. After obtaining written consent and signatures from the patients, the study was initiated.

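### Intention-to-treat is rejected while women are removed after randomisation, some for refusing the light, so the 36 versus 36 comparison is not protected by randomisation

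*Combined protocol and SAP*

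**What the plan says.** The Data analysis section states that "the intention-to-treat method was not used in the analyses". The reason given is "To ensure the balance between the groups and the reliability of the intervention results". It names no all-randomised analysis, no method for missing outcomes and no sensitivity analysis.

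Study design and participants gives the flow. It reports "a total of 89 women, 47 in the intervention group and 42 in the control group, were included in the study through randomization". It then says: "However, six women from the intervention group and three from the control group were excluded from the study because of various reasons". The reasons listed are "rejecting white light administration, familial reasons, and reaching saturation in stratification according to the fatigue level factor", pooled over arms and without counts. The study is then said to have been conducted "with a total of 72 women with 36 in each group".

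Randomization and blinding explains the equal numbers: assignment went on until each arm held 12 women in each of three fatigue strata. Under Interventions, both arms get energy-conservation and nutrition advice, but only the intervention arm gets the light.

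**The concern.** Refusing the light can remove a woman from the intervention arm only, because no control was offered it. The comparison is therefore between women who accepted the light and controls who were never put to that choice. If refusers would have had different day 9 or day 21 fatigue from acceptors, removing them moves the light-arm mean without any treatment effect, and controls undergo no matching removal for that reason.

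Neither stated justification answers this.

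- **Balance.** Twelve women per stratum per arm equalises baseline fatigue category and nothing else. Stratified block randomisation already aims at that, and a stratum term in the model handles what remains. Balance on all other factors is what randomisation provides, and removal linked to assignment can undo it.
- **Reliability.** The effect in women who accepted the light is a legitimate secondary question, but it is not a randomised comparison.

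The rule governs the trial's only between-arm comparison.

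**Working it through.** **1. The plan's own counts.** Inputs are from Study design and participants: 47 and 42 randomised, 6 and 3 excluded, 36 and 36 analysed.

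- Randomised: 47 + 42 = 89, as stated.
- After the stated exclusions: 47 − 6 = 41 and 42 − 3 = 39, total 80. The stated figure is 72, so it is not reproduced.
- If 89 and 72 are both right: 89 − 72 = 17 not analysed, of whom 17 − 9 = 8 have no reason in the text (light 11 − 6 = 5, control 6 − 3 = 3).
- The step before randomisation does not close either: 132 − 25 − 12 = 95, against 89.

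**2. Loss by arm.** The three post-randomisation figures cannot all be right. Taking two at a time, with a two-sided Fisher test:

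| Figures taken as right | Light arm lost | Control arm lost | p |
|---|---|---|---|
| 47/42 and 36/36 | 11/47 = 23.4% | 6/42 = 14.3% | 0.296 |
| 6/3 excluded and 36/36 (implies 42/39 randomised) | 6/42 = 14.3% | 3/39 = 7.7% | 0.485 |
| 47/42 and 6/3 excluded (implies 41/39 analysed) | 6/47 = 12.8% | 3/42 = 7.1% | 0.491 |

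Loss is higher in the light arm each time. None of the differences is significant, but that does not show the losses to be unrelated to outcome.

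**3. Illustrative shift.** If k of N light-arm women are removed and their outcome differs from that of the retained women by D (in SD), the light-arm mean shifts by (k/N) × D. D has no source in the documents, and excluded controls are assumed no different from retained ones.

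- k = 1, N = 47, D = 0.5: 0.011 SD
- k = 6, N = 42, D = 0.5: 0.071 SD
- k = 6, N = 47, D = 1: 0.128 SD
- k = 6, N = 42, D = 1: 0.143 SD

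This range is not a bound. If all 11 missing light-arm women differed by 1 SD, the shift would be 11/47 = 0.234 SD.

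**4. Effect on the test.** At 36 versus 36 the standard error in SD units is √(2/36) = 0.236. A shift of 0.128 SD is 0.128/0.236 = 0.54 standard errors. A nominal two-sided 5% normal test then rejects a true null about 8.4% of the time. At 0.234 SD the rate is about 16.8%.

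**5. Scale.** The plan says: "This study was based on an effect size of 0.25". It names no metric. Against it, 0.143 SD is 0.143/0.25 = 57% if 0.25 is a standardised mean difference, or 0.143/0.50 = 29% if it is Cohen's f (d = 0.5 for two groups). This gives scale only, and the conclusion does not rest on it.

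**6. Would a mixed model alone cure it?** A simulation took 47 versus 42 women, with 11 light and 6 control women having day 1 data only. It assumed between-visit correlations of 0.3 to 0.7 and used a random-intercept model without a stratum term, with 200 trials per setting. With 6 refusers 1 SD worse after baseline, the all-randomised contrast averaged 0.11 to 0.14 SD. The mixed model and the 36 versus 36 contrast both averaged −0.01 to 0.01 SD. If excluded women have no follow-up scores, the model recovers none of the shift.

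**The case against.** The strongest reply is that the extent of selective removal is unknown. Three reasons are pooled over nine women, so the text shows only that refusal of the light occurred. Many removals may be women randomised into a stratum that was already full. If those depended only on baseline stratum and order of entry they may be harmless, and they could account for some of the eight women without a reason. Family reasons could apply in either arm. The 0.14 SD figure needs all six light-arm exclusions to be refusals and uses 42 rather than the stated 47 randomised. The flow figure is not shown in this copy and may settle the counts.

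All of this stands as a limit on magnitude. It does not rescue the rule: a flow chart can reconcile numbers, but it cannot make a comparison of acceptors with all controls a randomised one.

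A second objection also stands in part. The documents do not say whether day 9 or day 21 scores exist for excluded women, and the choice of a mixed model is partly preference. What is essential is the analysis population and a stated missing-data method.

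**Conclusion.** The concern holds. The rejection of intention-to-treat is explicit, at least one reason for removal is specific to the light arm, and neither stated justification is sound. Between 9 and 17 randomised women are left out, depending on which counts are right.

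Confidence is high that the rule is wrong as written. It is not high that a material bias occurred: the number of refusers, their outcomes and the direction of any bias are not in the documents. The shifts in SD rest on assumed outcome gaps and on excluded controls being no different from those retained.

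**What to change.** 1. Make the primary analysis all randomised women in their assigned arm. Use every available day 1, 9 and 21 score in a likelihood-based mixed model with arm, time and arm-by-time, adjusted for fatigue stratum. Randomization and blinding says "patients who met the inclusion criteria and accepted to participate in the study were stratified according to the severity of fatigue" before assignment, so stratum should exist for every randomised woman.
2. Add a delta-adjusted sensitivity analysis for women without follow-up scores, from −1 to +1 SD (a chosen range), once in the light arm only and once in both arms, and report the tipping point. In the order of the table above, the contrast would span ±0.234, ±0.143 or ±0.128 SD for the light arm only, and ±0.091, ±0.066 or ±0.056 SD with the same delta in both arms. If only day 1 data exist, this analysis carries the weight.
3. Label the 36 versus 36 set as secondary (per-protocol or completer).
4. Reconcile the flow and report losses by arm and reason, including how many women refused the light and how many were removed because a stratum was full.

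The cost is one re-analysis, retrieval of whatever scores exist for 9 to 17 women, and a corrected flow chart. No new patients are needed. The arms will no longer be exactly equal, the estimate may be smaller, and it will depend on missing-data assumptions. If only day 1 scores exist, the point estimate will barely move and the gain is an honest range around it.
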